6.11.4.2 Central monitoring at NCTU

NCTU staff will review electronic Case Report Form (eCRF) data for errors and missing key data points. The trial database will also be programmed to generate reports on errors and error rates. Essential trial issues, events and outputs, including defined key data points, will be detailed in the trial Data Management Plan.

6.11.4.3 On-site monitoring

A risk-based monitoring approach will be adopted, and on-site monitoring is not expected to be undertaken unless central monitoring processes flag concerns. The frequency, type and intensity of triggered on-site monitoring will be detailed in the PROTECT Quality Management and Monitoring Plan (QMMP). The QMMP will also detail the procedures for review and sign-off of monitoring reports. In the event of a request for a trial site inspection by any regulatory authority, NCTU must be notified as soon as possible.

6.11.4.3.1 Direct access to participant records

Participating investigators must agree to allow trial related monitoring, including audits, REC review and regulatory inspections, by providing access to source data and other trial related documentation as required. Participant consent for this will obtained as part of the informed consent process for the trial.

6.11.4.4 Trial oversight

Trial oversight is intended to preserve the integrity of the trial by independently verifying a variety of processes and prompting corrective action where necessary. The processes reviewed relate to participant enrolment, consent, eligibility, and allocation to trial groups; adherence to trial interventions and policies to protect participants, including reporting of harms; completeness, accuracy and timeliness of data collection; and will verify adherence to applicable policies detailed in the compliance section of the protocol. Independent trial oversight complies with the NCTU trial oversight policy.

In multi-centre trials this oversight is considered and described both overall and for each recruiting centre by exploring the trial dataset or performing site visits as described in the PROTECT Quality Management and Monitoring Plan.

6.11.4.4.1 Trial Team

The Trial Team (TT) will be set up to assist with developing the design, coordination, and day to day operational issues in the management of the trial, including budget management. The Trial Team will comprise the CIs and UEA trial management team, who will meet 1-2 weekly..

6.11.4.4.2 Trial Management Group

A Trial Management Group (TMG) will be set up to assist with developing the design, coordination, and strategic management of the trial. The membership, frequency of meetings, activity (including trial conduct and data review) and authority will be covered in the TMG terms of reference.

6.11.4.4.3 Trial Steering Committee

The Trial Steering Committee (TSC) is the group responsible for oversight of the trial, in order to safeguard the interests of trial participants. The TSC provides advice to the CI, NCTU, the funder and sponsor on all aspects of the trial through its independent Chair. The membership, frequency of meetings, activity (including trial conduct and data review) and authority will be covered in the TSC terms of reference.

6.11.4.4.4 Data Monitoring Committee

The Data Monitoring Committee (DMC) is the only oversight body that has access to unblinded accumulating comparative data. The DMC comprises independent members and is responsible for

safeguarding the interests of trial participants, monitoring the accumulating data, and making recommendations to the TSC on whether the trial should continue as planned. The membership, frequency of meetings, activity (including review of trial conduct and data) and authority will be covered in the DMC terms of reference. The DMC will consider data in accordance with the statistical analysis plan and will advise the TSC through its Chair.

6.11.4.4.5 Trial Sponsor

The UEA is the trial sponsor. The role of the sponsor is to take on responsibility for securing the arrangements to initiate, manage, and finance the trial. The Sponsor is responsible for ensuring that the study meets the relevant standards and makes sure that arrangements are put and kept in place for management, monitoring and reporting. The UEA has delegated some Sponsor's activities to the CI and NCTU, these are documented in the Sponsor's form for delegated activities.

7 Safety reporting

Definitions of the EU Directive 2001/20/EC Article 2 based on the principles of ICH GCP apply.

Table 2: Adverse event definitions

[figure not shown]
Adverse Event (AE)	Any untoward medical occurrence, unintended disease or injury, or untoward
Adverse Event (AE)	clinical signs (including an abnormal laboratory finding) in a participant, whether or not related to the intervention.
	This definition includes events related to the intervention, the comparator, and the study procedures.
Adverse events includ	e: on of a pre-existing illness
 a condition (relation trial procedure) continuous p 	the frequency or intensity of a pre-existing episodic event or condition egardless of whether present prior to the start of the trial) that is detected after es / intervention. (This does not include pre-existing conditions recorded as such ersistent disease or a symptom present at baseline that worsens following n of the trial treatment
• Pre-existing d	rgical procedures: the condition that leads to the procedure is the adverse event isease or a condition present before treatment that does not worsen in where no untoward or unintended response has occurred e.g., elective
Serious Adverse	Any AE that:
Event (SAE)	 results in death is life threatening* requires hospitalization or prolongs existing hospitalization** results in persistent or significant disability or incapacity is a congenital anomaly or birth defect is otherwise considered medically significant by the investigator

* The term life threatening here refers to an event in which the patient is at risk of death at the time of the event; it does not refer to an event that might hypothetically cause death if it was more severe

** Hospitalization is defined as an in-patient admission, regardless of length of stay, even if the hospitalization is a precautionary measure for continued observation. Hospitalization for pre-existing conditions (including elective procedures that have not worsened) or planned hospitalization for a pre-existing condition or a procedure required by the protocol without serious deterioration in health do not constitute SAEs.

7.1 Investigator responsibilities relating to safety reporting

Participants will be reviewed for adverse events at all study visits. Non-serious AEs do *not* need to be reported to NCTU, however should be recorded per local policies. SAEs and Adverse Events of Special Interest (AESI), should be reported to NCTU in line with the below:

7.1.1 Adverse Events of Special Interest

The following Adverse Events of Special Interest (AESI) should be reported using the relevant eCRF:

Severe hypoglycaemia: An event requiring assistance of another person actively to administer carbohydrate, glucagon, or other resuscitative actions. Severe hypoglycaemia will be categorised as treated at home with rescue carbohydrates and/or glucagon, requiring ambulance or paramedic call out, and/or requiring hospital admission.

Hyperosmolar hyperglycaemic state (HHS) / Diabetic ketoacidosis (DKA): requiring hospital admission and treated with intravenous insulin infusion (as defined by the Joint British Diabetes Societies).

7.1.2 Seriousness assessment

When an AE occurs, the investigator responsible for the care of the participant must assess whether or not the event is 'serious' using the definition given in Table 2.

The following ARE considered Serious Adverse Events:

- Severe maternal hypoglycaemic event requiring paramedic assistance, emergency department assessment and/or hospital admission.
- Admissions with HHS/DKA requiring inpatient treatment with fixed or variable rate intravenous insulin infusion
- Maternal death
- Stillbirth / neonatal death
- Severe skin reaction requiring hospital admission
 - Note: Itchiness, redness, bleeding, and bruising at the insertion site may occur as well as local tape allergies. Only where a skin reaction is classified as potentially lifethreatening and requiring hospital admission will a Serious Adverse Event Form be required to be completed.

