7.1.3 Exempted Serious Adverse Events

The following are likely to be related to the underlying condition or disease or likely to represent concomitant illness and **will not be considered to be reportable as SAEs** in this study:

- Hospitalization for fetal monitoring during delivery, or hospitalization for delivery (including preterm delivery)
- Hospitalisation for unstable blood glucose/increased hypoglycaemia, and decreased insulin requirements, necessitating fetal monitoring and delivery.
- Hospitalization for maternal indications common to type 2 diabetes pregnancy:
 - Hypertensive disorders of pregnancy (gestational hypertension, worsening of preexisting hypertension, preeclampsia)
 - o Hyperemesis
 - o Pregnancy loss: miscarriage or termination before 24 weeks
 - Severe adverse peripartum outcomes: abruption, post-partum haemorrhage, 3rd degree tears, postnatal readmission with wound complications
 - Other obstetric reason for admission unrelated to diabetes
 - Preterm labour or birth
 - Severe hypoglycaemia without paramedic call-out, emergency department assessment or hospital admission
 - Admission for hyperglycaemia or ketosis not requiring treatment with fixed or variable rate intravenous insulin infusion
- Infant outcomes known to type 2 diabetes pregnancy:
 - o Birth injury
 - Congenital or chromosomal anomalies
 - Admission to neonatal unit
 - Neonatal hypoglycaemia (including hypoglycaemic seizures)
 - Hyperbilirubinemia
 - Respiratory distress
 - Shoulder dystocia

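### The note on skin reactions in section 7.1.2 requires an SAE form only for events that are both potentially life-threatening and admitted, which contradicts its own bullet, Table 2 and section 7.3.1; a narrower overlap exists for severe hypoglycaemia

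*Protocol*

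**What the plan says.** **General rule.** Table 2 in section 7 gives alternative criteria for an SAE, any one of which is enough. One is that the event "requires hospitalization or prolongs existing hospitalization"; another is that it is life-threatening. The footnotes settle both terms. "Hospitalization is defined as an in-patient admission, regardless of length of stay", and life-threatening means real danger of death when the event occurs: "it does not refer to an event that might hypothetically cause death if it was more severe". Section 7.3.1 requires an SAE form for any event that meets Table 2.

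**Skin reactions.** Section 7.1.2 lists as an SAE: "Severe skin reaction requiring hospital admission". The note beneath limits the SAE form to cases where the "skin reaction is classified as potentially lifethreatening and requiring hospital admission".

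**Hypoglycaemia.** Section 7.1.2 also lists: "Severe maternal hypoglycaemic event requiring paramedic assistance, emergency department assessment and/or hospital admission". Section 7.1.3 names events that are not to be reported as SAEs, among them: "Hospitalisation for unstable blood glucose/increased hypoglycaemia, and decreased insulin requirements, necessitating fetal monitoring and delivery".

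**Other routes.** Under section 7.1, non-serious events are not reported to the trials unit. The AESI list in 7.1.1 covers severe hypoglycaemia, the hyperosmolar hyperglycaemic state and ketoacidosis. It does not cover skin reactions.

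**The concern.** The note joins two criteria that Table 2 treats as alternatives, and so narrows the bullet it is meant to explain. An investigator who reads the bullet files a form; one who reads the note does not.

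Several steps depend on that form:
- the causality assessment (7.1.4, which applies to reportable SAEs only)
- review by a Co-Chief Investigator, and the report to the manufacturer when the event is related to the CGM system (7.3.2)
- the report to the ethics committee within 15 days when the event is related and unexpected (7.3.2)
- the data monitoring committee's review of SAEs by arm (6.11.3)

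Skin reactions are absent from the expected events in 7.1.6, so an admitted device reaction could qualify for the ethics committee report. Following the note would stop that before it starts. On-site monitoring is not expected unless central monitoring raises a concern (6.11.4.3), so a form that was never filed is unlikely to be found on a site visit.

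For hypoglycaemia the problem has the same kind but a smaller reach: one event can be both a listed SAE and an exempt one, and nothing says which section prevails.

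**Working it through.** No figure in the protocol is at issue, so the check applies each rule to the same event.

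| Event | Table 2 | 7.1.2 list | 7.1.2 note | 7.1.3 | 7.3.1 | Conflict |
|---|---|---|---|---|---|---|
| 1. Severe skin reaction, admitted, not life-threatening | serious | SAE | no form | not exempt | form | yes |
| 2. Life-threatening skin reaction, not admitted | serious | not listed | no form | not exempt | form | yes |
| 3. Severe hypoglycaemia, admitted, falling insulin requirements, leading to fetal monitoring and delivery | serious | SAE | does not apply | exempt | form | yes |
| 4. Severe hypoglycaemia, admitted, without that sequence | serious | SAE | does not apply | not exempt | form | no |
| 5. Severe hypoglycaemia treated at home | not serious by admission | not listed | does not apply | exempt | form only if another Table 2 criterion is met | none between 7.1.2 and 7.1.3 |

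**Events 1 and 2.** No reading satisfies all the rules, because the note begins with a restriction to one kind of case. Its wording also differs from Table 2: the note speaks of a potential threat to life, while the Table 2 footnote excludes hypothetical risk.

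**Event 3.** The exemption does not exclude severe events. Section 7.3.1 ties the form to Table 2 without mentioning the exemptions, so it adds a second conflict.

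**Exposure by arm.** Inputs:
- 14-day sensors until after delivery in the CGM arm (6.4.1.3)
- masked sensors at 20, 28, 32 and 36 weeks in the control arm (6.4.2.1)
- randomisation by 16+0 weeks (6.6.1.2)
- median delivery at 38 weeks (6.10.4.1)
- 211 women per arm (2.3)

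Assume one sensor at a time from 16+0 weeks and no failures.

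- CGM arm after randomisation: (38 − 16) / 2 = 11 sensors per woman; 11 × 211 = 2,321.
- Control arm after randomisation: 4 sensors per woman; 4 × 211 = 844.
- Ratio: 11 / 4 = 2.75.
- SAE reporting runs from consent (7.3.1), and both arms wear a masked baseline sensor (6.6.1.1). Adding it gives (11 + 1) / (4 + 1) = 12 / 5 = 2.4.

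Control women who wear their own CGM beside the masked sensor (6.6.1.6) would lower the ratio further. It counts insertions, not reactions.

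**The case against.** Several points against the concern are sound.

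**Skin events have other routes.** A reader might infer that an admitted skin reaction cannot reach the trials unit at all. The protocol does not support that. Section 7.1.2 opens by sending the investigator to Table 2, and 7.3.1 requires a form when Table 2 is met. Hospital admission is also collected as visit and delivery data (6.6) and is a secondary outcome (6.5.2). This stands. It does not remove the contradiction, because a site that follows the note files no form, and admission data carry no causality assessment.

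**The hypoglycaemia overlap is narrow.** A reader might infer that hypoglycaemia admissions in general are both reportable and exempt, for example any ambulance admission followed by delivery. That is not shown. The exemption also needs decreased insulin requirements that necessitate fetal monitoring and delivery. Another line of 7.1.3 exempts severe hypoglycaemia only when there was no call-out, emergency assessment or admission, which agrees with 7.1.2. The amendment log presents the disputed line as a clarification about admissions for fetal monitoring or delivery. What remains is event 3.

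**Little is lost for hypoglycaemia.** Severe hypoglycaemia is an AESI with admission as a category (7.1.1) and is compared by arm (6.10.4.3). It is on the expected list (7.1.6), so the ethics committee report, which needs an unexpected event, would not apply. This stands: only the SAE form, its causality review and its timeline are at stake.

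**An exemption list is not itself a contradiction.** Such lists exist to remove serious events from reporting. True, but here one event is named in both lists without a rule of precedence.

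**Conclusion.** The contradiction over skin reactions is direct and certain on the protocol's text. Table 2, the 7.1.2 bullet and 7.3.1 require a form for a severe reaction that leads to admission; the note does not. A site following the note would send no safety report for an event that is neither an AESI nor on the expected list. The hypoglycaemia overlap is real but confined to severe admissions with falling insulin requirements that lead to fetal monitoring and delivery, and those remain recorded as AESIs.

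The number of events affected cannot be derived, because the protocol gives no event rates. The insertion ratio of about 2.4 to 2.75 shows only that any under-reporting of skin events would fall on arms with unequal sensor exposure. It would be tempting to read it as a multiple of lost events, or to say that the by-arm safety table will change; neither follows. The ratio rests on the assumptions shown, and control-arm CGM use would lower it. No primary outcome is affected. The passages should be reconciled because the inconsistency bears on safety reporting and is cheap to remove.

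**What to change.** 1. Reconcile the 7.1.2 note with its bullet, Table 2 and 7.3.1. One way is to delete the life-threatening condition from the note, so that admission alone triggers the form, as in the protocol's own definition of seriousness. A life-threatening reaction without admission would then still need a form under Table 2 and 7.3.1, so the note should not be worded to exclude it.
2. State which of 7.1.2 and 7.1.3 takes precedence for a severe hypoglycaemia admission that fits both. The choice is the sponsor's; it needs to be written down.
3. Make 7.3.1 refer to the 7.1.3 exemptions, so that the rule for completing a form and the list of exempt events no longer conflict.
4. Re-query events already classified under the narrower lines. Existing AESI hypoglycaemia records and recorded hospital admissions are the starting points.

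The cost is a short wording amendment, a memo to sites, one round of queries and a few more SAE forms.

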7.1.3 Exempted Serious Adverse Events

The following are likely to be related to the underlying condition or disease or likely to represent concomitant illness and **will not be considered to be reportable as SAEs** in this study:

- Hospitalization for fetal monitoring during delivery, or hospitalization for delivery (including preterm delivery)
- Hospitalisation for unstable blood glucose/increased hypoglycaemia, and decreased insulin requirements, necessitating fetal monitoring and delivery.
- Hospitalization for maternal indications common to type 2 diabetes pregnancy:
 - Hypertensive disorders of pregnancy (gestational hypertension, worsening of preexisting hypertension, preeclampsia)
 - o Hyperemesis
 - o Pregnancy loss: miscarriage or termination before 24 weeks
 - Severe adverse peripartum outcomes: abruption, post-partum haemorrhage, 3rd degree tears, postnatal readmission with wound complications
 - Other obstetric reason for admission unrelated to diabetes
 - Preterm labour or birth
 - Severe hypoglycaemia without paramedic call-out, emergency department assessment or hospital admission
 - Admission for hyperglycaemia or ketosis not requiring treatment with fixed or variable rate intravenous insulin infusion
- Infant outcomes known to type 2 diabetes pregnancy:
 - o Birth injury
 - Congenital or chromosomal anomalies
 - Admission to neonatal unit
 - Neonatal hypoglycaemia (including hypoglycaemic seizures)
 - Hyperbilirubinemia
 - Respiratory distress
 - Shoulder dystocia

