7.1.4 Causality

The investigator must assess the causality of all reportable serious adverse events in relation to the trial intervention or procedures using the definitions in Table 4.

Relationship	Description	
Unrelated	There is no evidence of any causal relationship	
Unlikely to be related	There is little evidence to suggest that there is a causal relationship. There is another reasonable explanation for the event (e.g. the participant's clinical condition or other concomitant treatment)	
Possibly related	There is some evidence to suggest a causal relationship. However, the influence of other factors may have contributed to the event (e.g., the participant's clinical condition or other concomitant treatment)	
Probably related	There is evidence to suggest a causal relationship and the influence of other factors is unlikely	
Definitely related	There is clear evidence to suggest a causal relationship and other possible contributing factors can be ruled out	

Table 3: Causality definitions

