7.1.6 Expectedness

If there is at least a possible relatedness to the trial intervention or procedures, the Chief Investigator must assess the expectedness of the event. An unexpected event is one that is not reported in the protocol, or one that is more frequently reported or more severe than previously reported.

The following are 'expected' maternal events:

- Hypoglycaemia (including severe hypoglycaemia)
- Hyperglycaemia, ketosis, HHS, DKA

The following are 'expected' events in the infant:

- Birth injury
- Congenital or chromosomal anomalies
- Admission to neonatal unit
- Neonatal hypoglycaemia (including hypoglycaemic seizures)
- Hyperbilirubinemia
- Respiratory distress
- Shoulder dystocia

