7.3 Notifications

7.3.1 Notifications by the Investigator to NCTU

If the event meets the criteria for 'serious' (Table 2) then a SAE form must be completed and forwarded to NCTU. This should be **immediately, and in no circumstances later than 3 calendar days** after the Investigator becomes aware of the event.

Investigators should notify NCTU of related SAEs occurring from consent until maternal post-partum hospital discharge. If the participant discontinues with the intervention, SAEs considered related to the intervention should still be reported.

The SAE form must be signed off by the Principal Investigator (PI) or other investigator with delegated responsibility, with attention paid to the severity and causality of the event. In the absence of the PI (or delegate), the SAE form should be completed and signed by a member of the site trial team and emailed as appropriate within the timeline. The PI/delegate should check the SAE form at the earliest opportunity, make any changes necessary, sign and then email to NCTU. Detailed written reports should be completed as appropriate. Systems will be in place at the site to enable the PI to check the form for clinical accuracy as soon as possible.

The minimum criteria required for reporting an SAE are the trial number and date of birth, name of reporting person and sufficient information on the event to confirm seriousness. Any further information regarding the event that is unavailable at the time of the first report should be sent as soon as it becomes available.

The SAE form must be scanned and sent by email to the NCTU central safety email account ([contact]).

Participants must be followed up until clinical recovery is complete / laboratory results have returned to normal or baseline values, or until the event has stabilised. Follow-up should continue after completion of protocol intervention and/or trial follow-up if necessary. Follow-up SAE forms (clearly marked as follow-up) should be completed and emailed to NCTU as further information becomes available. Additional information and/or copies of test results etc. may be provided separately. The participant must be identified by trial number, date of birth and initials only. The participant's name should not be used on any correspondence and should be blacked out and replaced with trial identifiers on any test results.

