7.3.2 Reporting procedures for SAEs

A Co-Chief Investigator (or a medically qualified delegate) will review all SAE reports received. In the event of disagreement between the causality assessment given by the local investigator and the Co-CI (or delegate), both opinions and any justifications will be provided in subsequent reports.

The delegated staff at NCTU will cross reference the SAE against expected events specified in the protocol to determine onward reporting requirements. This expectedness assessment will be reviewed and signed off by a Co-Cl.

SAEs considered to be related to the CGM system will be reported to the manufacturer in line with the contract.

SAEs should be reported to the main REC within 15 days of the NCTU becoming aware if, in the opinion of the CI, the event was both:

- Related to the study i.e., resulted from the administration of the CGM or trial procedures
- Unexpected i.e., not listed in the protocol as an expected occurrence.

NCTU will keep investigators informed of any safety issues that arise during the course of the trial.

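### The SAE exemptions in section 7.1.3 have no exception for events attributed to the CGM system, and they conflict with sections 7.3.1 and 7.1.6 on whether such events are reported

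*Protocol*

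**What the plan says.** **Exemption.** Protocol section 7.1.3 gives its reason as a statement about types of event: "The following are likely to be related to the underlying condition or disease or likely to represent concomitant illness". The listed events then "will not be considered to be reportable as SAEs". The list covers maternal admissions, pregnancy loss before 24 weeks, peripartum complications and seven infant events. One entry is "Hospitalisation for unstable blood glucose/increased hypoglycaemia, and decreased insulin requirements, necessitating fetal monitoring and delivery". Another is admission for hyperglycaemia or ketosis that did not need intravenous insulin. No entry depends on what the investigator thinks caused the event.

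**Causality.** Section 7.1.4: "The investigator must assess the causality of all reportable serious adverse events in relation to the trial intervention or procedures".

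**Expectedness.** Section 7.1.6: "If there is at least a possible relatedness to the trial intervention or procedures, the Chief Investigator must assess the expectedness of the event". Two lists of expected events follow, one maternal and one infant.

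**Notification.** Section 7.3.1: "If the event meets the criteria for 'serious' (Table 2) then a SAE form must be completed and forwarded to NCTU", and further on: "Investigators should notify NCTU of related SAEs occurring from consent until maternal post-partum hospital discharge". Neither sentence refers to the exemptions.

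**Onward reporting.** Under section 7.3.2 a Co-Chief Investigator or delegate reviews the SAE reports that arrive, and "SAEs considered to be related to the CGM system will be reported to the manufacturer in line with the contract". The ethics committee is told of SAEs that are both related and unexpected.

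**The concern.** An exemption list normally spares sites from filing forms for complications that are common in the condition. This one fixes the cause in advance for whole classes of event, and the investigator has no stated way to say that a particular case was different.

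That matters for a glucose-monitoring device. Some exempt events are plausible consequences of wrong or lost readings: admission for unstable glucose leading to delivery, or admission with hyperglycaemia or ketosis. If a site treats the exemption as final, its judgement that the device was at fault is not recorded on any safety form, nobody reviews it centrally, and the manufacturer route in 7.3.2 is not triggered. If another site follows 7.3.1, the same event is reported. Sites could then handle identical events differently while each follows part of the protocol.

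**Working it through.** The plan states no figure on this point. The check sets the sections side by side.

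**1. The two lists.** The infant events in 7.1.3 are birth injury, congenital or chromosomal anomaly, neonatal unit admission, neonatal hypoglycaemia, hyperbilirubinaemia, respiratory distress and shoulder dystocia. The infant events in 7.1.6 are the same seven (7 of 7). Expectedness is assessed only once an event is at least possibly related. If the exemption is absolute, these seven never reach that step and the infant list has no use. If the list is meant to be used, 7.1.3 lacks an exception.

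**2. One event under each reading.** Take a CGM-arm woman admitted with ketosis, no intravenous insulin given, where the investigator blames the sensor. The admission makes it serious by Table 2.

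| Step | Site follows 7.1.3 | Site follows 7.3.1 |
|---|---|---|
| SAE form | none | yes |
| Causality recorded (7.1.4) | not required | yes |
| Central review (7.3.2) | nothing received | yes |
| Manufacturer route (7.3.2) | not triggered | yes |
| Ethics committee (7.3.2) | no | normally no, because ketosis is on the expected list |

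**3. Can 7.3.1 simply prevail?** Its first sentence, taken literally, asks for a form for every Table 2 event and so cancels 7.1.3. For scale, take the design figures in section 6.7 and 211 women per arm. Neonatal unit admissions alone would be 211 × 0.422 = 89.0 in the control arm and 211 × 0.260 = 54.9 in the CGM arm, about 144 forms in total. This assumes one baby per woman, no drop-out, and that such an admission counts as hospitalisation under Table 2. Removing that workload is evidently what 7.1.3 is for, so the literal reading is unlikely to be intended. The second sentence covers related SAEs only, but it relies on a causality judgement that 7.1.4 asks for only when the event is reportable.

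**4. Ethics committee route.** I take the 7.1.6 lists as the expected occurrences that 7.3.2 refers to. The seven infant events, and hypoglycaemia, hyperglycaemia and ketosis in the mother, are on them. Even if reported and judged related, they would normally stop there, unless more frequent or more severe than previously reported. Preterm birth, abruption and hypertensive disorders are exempt but not on the expected lists. For those the exemption could decide whether the committee is told.

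**5. An overlap.** An admission for increased hypoglycaemia is exempt under 7.1.3 when it leads to fetal monitoring and delivery. Severe maternal hypoglycaemia with hospital admission is an SAE under 7.1.2. One event can meet both descriptions, and no precedence is given.

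**The case against.** The strongest reply is that the protocol does provide for related events. Section 7.3.1 asks for them and does not mention the exemptions. Section 6.6.1.11 keeps follow-up of CGM- or study-related SAEs after early pregnancy loss. The presence of exempt infant events on the 7.1.6 list suggests that the authors expected related cases to get that far. This stands to the extent that non-reporting is not settled. A reader might infer from 7.1.3 that every exempt event blamed on the device is certain to be lost. The documents support only a contradiction, in which the specific and emphasised exemption is what a site would probably apply.

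A second reply is that the events are recorded anyway. This largely stands. Neonatal unit admission is part of the primary neonatal outcome (6.5.1). Birth injury, congenital anomaly, neonatal morbidity, maternal admissions and hypertensive disorders are secondary outcomes (6.5.2), and preterm birth is compared by arm (6.10.4.3). Severe hypoglycaemia managed at home is an adverse event of special interest (7.1.1), though no causality step is stated for those. A reader might infer that the safety comparison between arms would be falsely clean. It would not be on this account, because an excess in the CGM arm would still show in the outcome data.

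Third, the most obvious device harms stay reportable under 7.1.2: severe hypoglycaemia with paramedic, emergency department or hospital care, HHS or DKA needing intravenous insulin, and severe skin reactions with admission. That is correct and limits the gap.

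Fourth, manufacturer reporting follows a contract that is not among the documents, so another route for device faults cannot be excluded. That also stands. The point here is only that the protocol's own route starts from an SAE.

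**Conclusion.** The point holds as an internal contradiction with a practical consequence. Sections 7.1.3 and 7.1.4 together leave out serious events of the listed types whatever their cause. Sections 7.3.1 and 7.1.6 presuppose that related ones are reported. Nothing says which governs. Under 7.1.3, an exempt serious event attributed to the device or a trial procedure has no recorded causality assessment, no central review and no entry to the manufacturer route.

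The scope is limited in three ways:

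- Ethics committee reporting is affected only for exempt events off the expected lists. A reader might infer that the exemption blocks this route for all exempt events, but for the seven infant events and for maternal hypoglycaemia, hyperglycaemia and ketosis the expectedness rule would usually do so anyway.
- What is at risk is individual attribution and onward reporting, not the comparison between arms.
- The number of events cannot be derived. The 42.2% background rate of neonatal admission in section 6.7 says nothing about how many would be attributed to the device. Nor is every listed item necessarily serious by Table 2; home-treated severe hypoglycaemia, for example, need not be.

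The conclusion assumes that sites apply 7.1.3 as written and that no unseen document, such as a site manual or the supply contract, already settles the matter.

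**What to change.** Add to section 7.1.3: *These exemptions do not apply to an event that meets Table 2 and that the investigator considers at least possibly related to the CGM system or a trial procedure; such an event is reported as an SAE under 7.3.1.*

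Add a cross-reference to section 7.3.1 stating that its Table 2 trigger is subject to 7.1.3 as so amended. This removes the contradiction, keeps the exemption for ordinary complications and gives the infant list in 7.1.6 a use. The same amendment should state whether 7.1.2 or 7.1.3 governs reporting of an admission for hypoglycaemia that meets both descriptions.

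The cost is a short amendment, a note to sites, and a small number of extra SAE forms. The investigator has to consider relatedness when an exempt serious event occurs, but completes a form only if the answer is at least possible. For scale only, if an assumed 0 to 2% of the 211 CGM-arm women had such an event, the extra forms would number 0 to about 4 (0.02 × 211 = 4.2). The protocol gives no basis for that rate. The change concerns reporting only and leaves treatment and clinical management untouched.
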